6.3.15.2 Clinical Safety Laboratory Tests (hematology, biochemistry and urinalysis)

Laboratory values (hematology [Listing 16.2.8.2.1 (Part A) and Listing 16.2.8.2.2 (Part B)], biochemistry [Listing 16.2.8.1.1 (Part A) and Listing 16.2.8.1.2 (Part B)] and urinalysis [Listing 16.2.8.3.1 (Part A) and Listing 16.2.8.3.2 (Part B)]) will be listed for each study part by subject and study time point including changes from baseline (with the exception of urinalysis). The baseline for the laboratory values will be the results obtained on Day -1.

All values outside the clinical reference ranges will be flagged in the data listings. The abnormal values will be flagged with 'L' for values below the lower limit of the clinical reference range and 'H' for values above the upper limit of the clinical reference range and included in the listings. The Investigator will assess whether the values outside the clinical reference range are clinically significant and these will be reported as abnormal not clinically significant (NCS) or abnormal clinically significant (CS). Clinically significant laboratory values will be recorded by the Investigator as AEs. Shift from baseline of laboratory finding for hematology and clinical chemistry (Normal, Low NCS, Low CS, High NCS and High CS) will be summarized, using frequencies and percentages, for each laboratory test by cohort group and nominal time point within each study.

Screening serology [Listing 16.2.8.4.1 (Part A) and Listing 16.2.8.4.2 (Part B)], drug screen test [Listing 16.2.8.5.1 (Part A) and Listing 16.2.8.5.2 (Part B)], pregnancy test [Listing 16.2.8.6.1 (Part A) and Listing 16.2.8.6.2 (Part B)], Alcohol breath test [Listing 16.2.8.7.1 (Part A) and Listing 16.2.8.7.2 (Part B)] results will be listed.

Any laboratory parameters that are given as '<xx' or '>xx' in the database will be imputed with the absolute value of the number without the sign (e.g., <2.2 will be imputed as 2.2) for the calculation of the changes from baseline and for the descriptive statistics.

Descriptive statistics (n, mean, SD, median, minimum, maximum) for non-categorical data including hematology [Table 14.3.5.2.1 (Part A) Table 14.3.5.2.2 (Part B)] and biochemistry [Table 14.3.5.1.1 (Part A) and Table 14.3.5.1.2 (Part B)] and any quantitative urinalysis [Table 14.3.5.3.1 (Part A) and Table 14.3.5.3.2 (Part B)] will be presented for each study part, by cohort and time point for both

PAREXEL International Statistical Analysis Plan

observed values and changes from baseline. Urinalysis results (normal or abnormal) will also be tabulated.

Abnormal laboratory values will be listed using conventional and standard units [Listing 14.3.4.1.1 (Part A), Listing 14.3.4.1.2 (Part B), Listing 14.3.4.2.1 (Part A), Listing 14.3.4.2.2 (Part B), Listing 14.3.4.3.1 (Part A) and Listing 14.3.4.3.2 (Part B)]. Shift tables for hematology [Table 14.3.5.5.1 (Part A), Table 14.3.5.5.2 (Part B)] and biochemistry [Table 14.3.5.4.1 (Part A) and Table 14.3.5.4.2 (Part B)] will be constructed that show the change in quantitative laboratory values from baseline with each study part, and by cohort and nominal time point.

No change from baseline will be calculated for screening visits.

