### **3.5 Stopping Criteria for Dose Escalation**

Dosing will be stopped if 1 (or more) of the following apply. Depending on the nature of the AEs, it could be decided to investigate a lower dose level (intermediate between the current and the prior one) in the next group.

1. If 1 or more subjects experiences a study drug-related serious adverse event (SAE), unblinding of the subject(s) will be done. If the subject(s) was (were) on active treatment, dosing will be stopped.
2. If 2 subjects in 1 dose group show the following findings in 2 consecutive postdose measurements within 24 hours and if unblinding reveals that both subjects received active treatment, dosing will be stopped:
  - a. ALT or AST  $\geq 3 \times$  upper limit of normal (ULN) or,
  - b. ALT or AST  $\geq 2 \times$  ULN and ALT or AST  $\geq 5 \times$  baseline value or,
  - c. TBIL  $\geq 2 \times$  ULN
3. If 2 or more subjects in 1 cohort experience AEs of severe intensity or 4 or more subjects in 1 cohort experience AEs of moderate intensity, which are considered by the PI and/or Sponsor to be possibly or probably related to the investigational product, and of clinical concern, and if unblinding reveals that these subjects received active treatment, dosing will be stopped.

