### ***3.5.1 PK stopping criteria***

Due to the liver damage (higher ALT, ALP, GGT, and enlargement in common bile duct in liver) reported in one male dog following multiple dosing at 2000 mg/kg for 7 days, and NOAEL in male and female beagle dog at 1000 mg/kg/day for 14 days, the decision to escalate to the next planned dose will be based on review of PK exposure data from previous dose cohort(s). This will involve use of best available modeling practices of the observed AUC (i.e.,  $AUC_{\text{tau}}$  or  $AUC_{0-\infty}$ ) and  $C_{\text{max}}$  from each dose, resulting in a predictive distribution of AUC and  $C_{\text{max}}$  at higher dose levels. If predicted mean AUC and  $C_{\text{max}}$  for the next dose level is higher than 41.3 ug.h/mL and 9.3 ug/mL, respectively, then the dose escalation will stop and the Sponsor and PI will need to review the totality of data, including safety and PK before make any dose escalation decision. This PK stopping criteria are based on dog 2-Week study NOAEL exposure at 1000 mg/kg/day (the most conservative species and gender).

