#### 6.4.1.3.4 Adverse Events of Interest

An adverse event of interest (AEI) is an event which, in the evaluation of safety, has a special focus. An AEI is an AE (SAE or non-serious AE) which fulfils below defined AEI criteria:

- Potential Hy's law cases

Potential Hy's law, defined as  $\geq 3 \times$  ULN ALT with co-existing  $\geq 2 \times$  ULN bilirubin in the absence of  $\geq 2 \times$  ULN ALP, with no alternative explanation for the biochemical abnormality, must always be reported as an AE of interest (i.e., without waiting for any additional etiologic investigations to have been concluded). Follow-up information should then be reported if an alternative etiology is identified during investigation and monitoring of the subject.

AEI should be reported to the Sponsor/PAREXEL immediately (within 24 hours of the site being aware of the event).

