**Table 6-2: Laboratory Assessments**

Test Group	Analyte/Component	Test Group	Analyte/Component
Hematology:	erythrocytes mean corpuscular volume (MCV) mean corpuscular hemoglobin (MCH) neutrophils eosinophils basophils lymphocytes monocytes platelets leukocytes hemoglobin hematocrit	Urinalysis:	pH protein glucose ketone bilirubin blood nitrite
Clinical chemistry:	albumin creatinine glucose urea uric acid total bilirubin (TBIL) direct bilirubin total protein triglycerides (TG) total cholesterol low-density lipoprotein (LDL) cholesterol high-density lipoprotein (HDL) cholesterol	Liver enzymes:	alkaline phosphatase (ALP) aspartate aminotransferase (AST) alanine aminotransferase (ALT) gamma-glutamyl transpeptidase (GGT)
Electrolytes:	sodium potassium calcium chloride	Serological marker:	Hepatitis B surface antigen (HbsAg) Anti-Hepatitis A Virus Immunoglobulin M (HAV IgM) Anti-Hepatitis C Virus (HCV Ab) Anti-Human immunodeficiency virus (HIV Ab)

Test Group	Analyte/Component	Test Group	Analyte/Component
Urine drug and cotinine screening, alcohol breath test	Amphetamines Barbiturates Benzodiazepines Cannabinoids Cocaine Opiates Cotinine Alcohol		

Clinical significance of out-of-range laboratory findings is to be determined and documented by the Investigator/sub-Investigator who is a qualified physician. Clinically relevant changes will be recorded as AEs in the eCRF (see Section 6.4.1.2).

For safety laboratory tests, the total volume of blood drawn will be approximately 51 mL for subject in Part A SAD and approximately 51 mL for subject in Part B MAD. Additional safety samples may be collected if clinically indicated at the discretion of the Investigator.

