6.1.2 Safety Variables

6.1.2.1 *Adverse Events*

An adverse event is any untoward medical occurrence that occurs in a subject or clinical investigation subject administered a pharmaceutical product, and which does not necessarily have to have a causal relationship with this treatment. An AE can therefore be any unfavorable and unintended sign (including abnormal laboratory finding), symptom, or disease temporally associated with the use of an investigational product, whether or not considered related to the product.

All AEs will be coded using the latest available version **19.1** of the Medical Dictionary for Regulatory Activities (MedDRA).

A treatment-emergent adverse event (TEAE) is defined as an AE that begins or that worsens in severity after at least one dose of the study drug has been administered.

Any AEs with incomplete start and end dates/times will be treated as follows:

- Adverse events with unknown start and/or end times (but where the date is known) will be imputed with a time of 00:00 h for the tabulations but will be shown as NK:NK in the listings (where NK = Not Known).
- Adverse events with completely unknown start dates will be considered as treatment-emergent for the tabulations and will be shown as NK in the listings.

6.1.2.2 *Clinical Laboratory Tests*

The following safety laboratory parameters will be measured at the time points mentioned in the table of assessments in the CSP section 7.

- **Clinical chemistry:** albumin, creatinine, glucose, urea, uric acid, TBIL, total protein, triglycerides (TG), total cholesterol, low-density lipoprotein (LDL) cholesterol, and high-density lipoprotein (HDL) cholesterol.
- **Hematology:** erythrocytes, mean corpuscular volume (MCV), mean corpuscular hemoglobin (MCH), neutrophils, eosinophils, basophils, lymphocytes, monocytes, platelets, leukocytes, hemoglobin, and hematocrit.
- **Urinalysis:** pH, protein, glucose, ketone, bilirubin, blood, and nitrite.

PAREXEL International
Statistical Analysis Plan

- **Serological marker:** Hepatitis B surface antigen (HbsAg), Anti-Hepatitis A Virus Immunoglobulin M (HAV IgM), Anti-Hepatitis C Virus (HCV Ab) and Anti-Human immunodeficiency virus (HIV Ab).
- **Urine Drug and cotinine screening, alcohol breath test:** Amphetamines, Barbiturates, Benzodiazepines, Cannabinoids, Cocaine, Opiates, Cotinine, and Alcohol.
- **Electrolytes:** sodium, potassium, calcium, and chloride.

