6.3 Statistical Analysis Methods

6.3.1 Listings and Descriptive Statistics

All original and derived parameters as well as population characteristics will be listed and described using summary statistics. Frequency counts (number of subjects [n] and percentages) will be made for each qualitative variable. Descriptive statistics (n, mean, standard deviation [SD], median, minimum and maximum) will be calculated for each quantitative variable (unless otherwise stated). All listings will include repeated and unscheduled measurements.

Study Part A and Part B will be analyzed separately. For each part Tables, listings and figures will be generated separately.

The following rules will apply to any repeated measurements:

- If the repeated measurement occurs prior to study drug administration (in each treatment period if applicable) then the last obtained value (or last obtained set of triplicate measurements) prior to dosing will be used in the descriptive statistics and in the calculation of changes from baseline (for results measured in triplicate the mean of the triplicates will be used in the calculation of changes from baseline).

PAREXEL International

Statistical Analysis Plan

- If the repeated measurement occurs after study drug administration (in each treatment period if applicable) then the first (non-missing) value of any repeated measurements (or first set of triplicate measurements) will be used in the descriptive statistics and in the calculation of changes from baseline (for results measured in triplicate the mean of the triplicates will be used in the calculation of changes from baseline).
- If not otherwise specified, baseline refers to the last scheduled measurement (or mean of the set of triplicate measurements) before study drug administration (using the rules described above for repeated measurements).

All descriptive statistics will be presented by cohorts (dose). Subjects receiving placebo within each cohort will be presented as pooled treatment group.

All descriptive statistics will be presented by cohorts for measurements obtained during each treatment period. Descriptive statistics for all data obtained at Screening and follow-up will be presented.

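### No planned SAP table or figure counts subjects who meet the protocol's liver limits or potential Hy's law, and confirming repeat values stay out of the descriptive tables

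*SAP*

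**What the plan says.** **Protocol.** Section 3.5.1 ties its PK limits to a non-clinical finding: "Due to the liver damage (higher ALT, ALP, GGT, and enlargement in common bile duct in liver) reported in one male dog". Section 3.5, criterion 2, then sets the liver limits. It opens "If 2 subjects in 1 dose group show the following findings in 2 consecutive postdose measurements within 24 hours" and lists three levels:
- 2a: ALT or AST at least 3 x ULN
- 2b: ALT or AST at least 2 x ULN and at least 5 x baseline
- 2c: total bilirubin (TBIL) at least 2 x ULN

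Section 6.4.1.3.4 defines potential Hy's law as ALT at least 3 x ULN with bilirubin at least 2 x ULN, without ALP at or above 2 x ULN and with no other explanation. It says such a case "must always be reported as an AE of interest". No other adverse event of interest is named.

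**SAP.** Section 6.3.15.2 plans n, mean, SD, median, minimum and maximum by cohort and time point, for observed values and changes from baseline. For shifts it says: "Shift from baseline of laboratory finding for hematology and clinical chemistry (Normal, Low NCS, Low CS, High NCS and High CS) will be summarized". For a test repeated after dosing, section 6.3.1 says: "then the first (non-missing) value of any repeated measurements (or first set of triplicate measurements) will be used in the descriptive statistics". The same section puts repeated and unscheduled values in every listing and pools placebo subjects.

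**Parameter lists.** Protocol Table 6-2 includes "direct bilirubin" under clinical chemistry. The corresponding SAP list (6.1.2.2) runs "albumin, creatinine, glucose, urea, uric acid, TBIL, total protein, triglycerides (TG" and on to the lipids, without it.

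**The concern.** Safety is the primary objective, and the liver is the one organ for which the protocol sets numerical laboratory limits. The natural question for the study report is how many subjects at each dose crossed those limits, compared with pooled placebo. The SAP's tables use different scales: laboratory units by visit, and position relative to the reference range with the investigator's judgement of significance. They also look at one analyte at a time. The value that would confirm a criterion 2 finding is, by the first-value rule, kept out of the descriptive statistics. A reader would have to answer the question from individual listings.

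**Working it through.** The documents state no figure on this point, so there is nothing to reproduce. The check sets the protocol's limits beside the SAP's planned outputs (SAP sections 8 to 10) and adds some simple arithmetic.

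**1. What each limit needs and what the tables offer.**

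| Protocol limit | Needed to see it | Planned in tables |
|---|---|---|
| 2a, 2c | Count of subjects at a multiple of ULN | By-visit maximum (one value, laboratory units); High NCS / High CS |
| 2b | Ratio to the subject's own baseline, with a ULN multiple | Change from baseline as a difference |
| Two measurements within 24 h | Paired values within a subject | First value only |
| Potential Hy's law | ALT, bilirubin and ALP in the same subject | Separate summaries per analyte |

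The index has no ULN-multiple table, no combined ALT and bilirubin display, and no output for the adverse event of interest. The adverse event listing fields in SAP 6.3.15.1 include a flag for serious events but none for events of interest.

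**2. Shift categories.** Exclusion 3 requires liver tests at or below ULN for entry. For these analytes the shift table is therefore essentially Normal to High. Only the investigator's NCS/CS call separates 1.1 x ULN from 5 x ULN.

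**3. Timing of the confirming sample.** Scheduled postdose chemistry days are in Protocol 7.2.2 and 7.2.3.
- Part A, Days 2, 7 and 14: gaps of 5 x 24 = 120 h and 7 x 24 = 168 h.
- Part B, Days 2, 4, 8 and 14: gaps of 2 x 24 = 48 h, 4 x 24 = 96 h and 6 x 24 = 144 h.

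The shortest gap is 48 h; the one-day window on Day 14 does not change that. Two scheduled samples can never fall within 24 h. The second measurement must be a repeat or come from outside the fixed schedule.

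**4. Effect of the first-value rule.** If the first value at a visit already meets the limit, the table maximum reflects it, but the confirmation is absent. If the first value is 2.8 x ULN and the repeat 3.4 x ULN, the table maximum is 2.8 x ULN and the crossing of 3 x ULN does not appear. SAP 6.3.1 names descriptive statistics and changes from baseline. That the rule also governs the shift tables is an inference from their layout by nominal time point.

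**5. What the mean and maximum show.** There are six active subjects per cohort. The ALT level b of the unaffected subjects, in ULN units, is an assumption.
- One subject at 3 x ULN: mean = (3 + 5b)/6 = 0.83, 0.92, 1.00 and 1.17 for b = 0.4, 0.5, 0.6 and 0.8.
- Two subjects at 3 x ULN: mean = (6 + 4b)/6 = 1.27, 1.33, 1.40 and 1.53 for the same b.

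The mean stays at or below ULN with one case as long as b is at most (6 - 3)/5 = 0.6. With two cases it exceeds ULN for any positive b. The maximum is 3 x ULN in both situations, so it does not distinguish one affected subject from two, and two is the number on which criterion 2 turns.

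**The case against.** The strongest reply is that nothing is concealed, and that part stands. Listings carry repeated and unscheduled values, flag every out-of-range result, and include a separate abnormal biochemistry listing in Section 14 of the report (14.3.4.1.1 and 14.3.4.1.2). Clinically significant values become adverse events. A potential Hy's law case is itself an adverse event and reaches the adverse event outputs. Liver safety monitoring is a tabulated reason for discontinuation. With six active subjects per cohort, the listings are readable. Escalation and stopping rest on review of data during the study, not on report tables, and Protocol 8.6.3 promises no more than listings, flags and descriptive statistics.

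Four stronger readings are tempting but unsupported:
- A reader might infer that liver tests are summarised only as means. The median, minimum and maximum are planned too, and the shift tables separate High CS from High NCS.
- A reader might infer that a case could be hidden. The listings and adverse event routes above show otherwise.
- A reader might fault the ALP condition in the Hy's law definition because ALP was raised in the dog. The documents give no ULN multiple for that rise, and the definition contradicts nothing else in the protocol.
- A reader might infer that liver enzymes fall outside the shift tables because SAP 6.1.2.2 lists them apart from clinical chemistry. That grouping copies Protocol Table 6-2, where electrolytes are also separate, and the SAP's output sections use only hematology, biochemistry and urinalysis.

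The non-clinical signal is also limited. It is one dog at 2000 mg/kg, twice the stated no-effect level of 1000 mg/kg/day.

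The reply does not supply a count of subjects per dose at the protocol's limits, or a display of ALT and bilirubin within the same subject.

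**Conclusion.** The point holds as a reporting gap. No planned table or figure identifies or counts subjects who meet criterion 2a, 2b or 2c or potential Hy's law, and the descriptive tables cannot show the confirming measurement that criterion 2 requires. The information exists in flagged listings, so the cost falls on the reader. Per-dose counts must be rebuilt across up to 48 subjects in Part A and 40 in Part B (88 in all), with placebo pooled by hand from 6 x 2 = 12 and 5 x 2 = 10 subjects.

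The absence of these outputs and the 48-hour spacing are read directly from the documents. The cohort means rest on assumed ALT levels in unaffected subjects and are illustrative only. Subject protection and the stopping rules are unaffected. This is a worthwhile, inexpensive improvement to the reporting of the primary objective. The missing direct bilirubin is a separate, small omission from the SAP list.

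**What to change.** Amend SAP 6.3.15.2 to add, for each part and by cohort with pooled placebo:
- A table of subjects by worst postdose ALT, AST, ALP, GGT and TBIL in multiples of ULN, using scheduled, repeat, unscheduled and early-discontinuation samples.
- Rows in that table for criterion 2a, 2b and 2c and for potential Hy's law, exactly as the protocol defines them. The laboratory conditions can be derived from the data; the absence of another explanation comes from the adverse event record.
- One plot of each subject's peak ALT against peak TBIL, both in multiples of ULN.

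Add direct bilirubin to the list in SAP 6.1.2.2. No stopping or clinical rule changes.

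The cost is some SAP wording plus one table and one figure per part, from results and local reference ranges already collected. The one drawback is that worst-value counts include transient or laboratory-error elevations. The by-visit tables stay beside them, so those can be recognised.

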6.3.15.3 Vital Signs

Vital signs data will be listed [Listing 16.2.9.1.1 (Part A) , Listing 16.2.9.1.2 (Part B)] by subject for each study part by subject including subject number, time point, changes from baseline for supine measurements, flags for measurements outside the reference ranges and the corresponding Investigator assessment (CS or NCS)and repeat/unscheduled measurements. The mean of any triplicate assessments performed at a given time point will be used in all calculations of changes from baseline and in all tabulations. The baseline for each measurement will be the mean of the triplicate assessments obtained on Day -1.

Vital signs data will be summarized [Table 14.3.6.1.1 (Part A) and Table 14.3.6.1.2 (Part B)], descriptive statistics (n, mean, SD, median, minimum, maximum) for absolute values and changes from baseline will be presented by for each study part, by cohort and time point for both observed values and changes from baseline.

No change from baseline will be calculated for screening visits.

6.3.15.4 Twelve-Lead Electrocardiogram

All ECG parameters obtained from the ECG measurement will be listed [Listing 16.2.9.2.1 (Part A) and Listing 16.2.9.2.2 (Part B)] by subject for each study part by subject and time point including changes from baseline and repeat/unscheduled measurements. The mean of any triplicate assessments performed at a given time point will be used in all calculations of changes from baseline and in all tabulations. The baseline for each measurement will be the mean of the triplicate assessments obtained on Day -1.

PAREXEL International
Statistical Analysis Plan

All ECG parameters will be summarized [Table 14.3.6.2.1 (Part A) and Table 14.3.6.2.2 (Part B)], descriptive statistics (n, mean, SD, median, minimum, maximum) will be presented within each study part, and by cohort and time point for both observed values and changes from baseline.

No change from baseline will be calculated for screening visits.

